#### 6.1 Inclusion Criteria

Subjects are eligible to be included in the study only if all of the following criteria apply:

- 
- 101 Subject has provided informed consent prior to initiation of any study specific activities/procedures
- 102 Age  $\geq$  18 years at the time of the signing of informed consent
- 103 Multiple myeloma meeting the following criteria:
- Pathologically-documented diagnosis of multiple myeloma that is relapsed or is refractory (see [Section 12.9](#)) as defined by the following:
    - Relapsed after  $\geq$  3 lines of prior therapy that must include a PI, an IMiD, and a CD38-directed antibody in any order during the course of treatment OR refractory to PI, IMiD, and CD38-directed antibody.
  - Measurable disease, defined by 1 or more of the following at time of screening:
    - serum M-protein  $\geq$  0.5 g/dL measured by serum protein electrophoresis (SPEP)
    - urinary M-protein excretion  $\geq$  200 mg/24 hours
    - Involved sFLC measurement  $>$  10 mg/dL, provided that the sFLC ratio is abnormal as per IMWG response criteria
- 104 Eastern Cooperative Oncology Group (ECOG) performance status of  $\leq$  2
- 105 Life expectancy of at least 3 months as per investigator's judgment at time of screening
- 106 Hematological function without transfusion support (within 7 days from screening assessment) as follows:
- ANC  $\geq$   $1.0 \times 10^9$ /L (without growth factor support)
  - platelet count  $\geq$   $50 \times 10^9$ /L (without transfusions), but  $\geq$   $25 \times 10^9$ /L if the marrow is replaced by  $\geq$  50% myeloma (unless receiving anticoagulation therapy then platelet count must be  $>$   $50 \times 10^9$ /L)
  - hemoglobin  $\geq$  7.0 g/dL (transfusions permitted no later than 48 hours before screening)
- 107 Renal function as follows:
- calculated or measured creatinine clearance  $\geq$  30 mL/min using the Cockcroft-Gault equation or via 24-hour urine collection with plasma and urine creatinine concentrations, respectively
- 108 Hepatic function as follows:
- aspartate aminotransferase (AST) and alanine aminotransferase (ALT)  $<$  3 x upper limit of normal (ULN)
  - total bilirubin (TBIL)  $<$  1.5 x ULN (unless considered due to Gilbert's syndrome)

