#### **7.4 Dose Modification**

##### **7.4.1 Dose-cohort Study Escalation/De-escalation and Stopping Rules**

The DLT evaluation period (ie, DLT-evaluable period) will be the 4 weeks on AMG 420 treatment within the first treatment cycle, starting on day 1 (start of infusion). The DLT evaluation period may also be extended to assess events starting within the window in case the DLT definition is time dependent.

Treatment in AMG 420 cycle 1 will be considered complete and the subject will be DLT evaluable if the subject has completed the DLT evaluation period or experienced a DLT any time during the DLT evaluation period. A subject will be non-DLT evaluable if he/she drops out before completion of the DLT-evaluable period for reasons other than a

DLT. All available safety data for subjects who are non-DLT-evaluable will still be evaluated and considered in DLRT decisions (see also [Section 10.4.1.1.1.1](#)).

See [Section 5.2.1](#) for description of replacement of subjects.

A DLT will be defined as any of the events described below occurring in a subject during the DLT evaluation period unless clearly attributable to causes other than treatment with AMG 420. The CTCAE version 5.0 (see [Section 12.4](#)) will be used to assess toxicities/adverse events with the exception of CRS and TLS (see [Section 7.4.2.1.2.5](#) and [Section 12.12](#) for grading criteria of CRS and TLS, respectively).

- Death not clearly due to the underlying disease or extraneous causes.

Non-hematologic DLTs:

- Non-hematological adverse event grade 3 or higher, EXCEPT:
  - infection responding to antibiotic/anti-infective treatment within 48 hours
  - grade 3 fatigue or asthenia
  - grade 3 headache resolving to  $\leq$  grade 2 within 72 hours
  - grade 3 insomnia resolving to  $\leq$  grade 2 within 7 days
  - grade 3 fever resolving to  $\leq$  grade 2 within 72 hours
  - grade 3 nausea, vomiting, or diarrhea responding if successfully managed with optimal medical support and resolved within 72 hours
  - laboratory parameters of grade  $\geq$  3, not considered clinically relevant, and improved to grade  $\leq$  2 within 72 hours

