- Any subject meeting the criteria for Hy's Law case (ie, severe drug-induced liver injury [DILI]) will be considered a DLT. A Hy's Law case is defined as: AST or ALT values of  $\geq 3 \times$  ULN AND with serum TBIL level of  $> 2 \times$  ULN or international normalized ratio (INR)  $> 1.5$  without signs of cholestasis and with no other clear alternative reason to explain the observed liver-related laboratory abnormalities (see [Section 7.4.3](#) for hepatotoxicity management and [Section 12.7](#) for further explanation of Hy's law case and management of hepatic function).

Hematologic DLTs:

- febrile neutropenia grade 4
- febrile neutropenia grade 3 unless responding to antibiotic/anti-infective treatment within 48 hours
- grade 4 neutropenia lasting more than 5 days, grade 4 thrombocytopenia lasting more than 7 days, grade 3 thrombocytopenia with hemorrhage or required platelet transfusion, or grade 4 anemia in the absence of detectable multiple myeloma as it may reflect a marrow toxic effect of AMG 420

The dosing schedule is described in the Schedule of Activities ([Section 2.2](#)).

---

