b High dose vasopressors (all doses are required for  $\geq 3$  hours): norepinephrine monotherapy  $\geq 20 \mu\text{g}/\text{min}$ , dopamine monotherapy  $\geq 10 \mu\text{g}/\text{kg}/\text{min}$ , phenylephrine monotherapy  $\geq 200 \mu\text{g}/\text{min}$ , epinephrine monotherapy  $\geq 10 \mu\text{g}/\text{min}$ ; if on vasopressin, vasopressin + norepinephrine equivalent of  $\geq 10 \mu\text{g}/\text{min}$ ; if on combination vasopressors (not vasopressin), norepinephrine equivalent of  $\geq 20 \mu\text{g}/\text{min}$ .

c All sites will ensure that CRS rescue medications are available on-site, including corticosteroids and (for sites in regions where tocilizumab is approved and available, eg, the US and Germany) 2 doses of tocilizumab per study subject.

#### 7.4.2.1.3 Permanent Discontinuation of AMG 420

AMG 420 treatment will be permanently discontinued in the event of:

- infusion-related reaction grade 4 (the infusion has to be stopped immediately)
- grade 4 CRS
- grade 2 or 3 CRS meeting any of the criteria listed below:
  - grade 2 or 3 CRS that does not improve to  $\leq$  grade 1 within 7 days
  - grade 3 CRS that does not improve to  $\leq$  grade 2 within 5 days
  - if a subject experiences 2 separate grade 3 CRS events
  - if a subject experiences repeat grade 2 CRS event after dose reduction
  - grade 3 CRS at the initial run-in dose of the first treatment cycle if a dose step is being used
- grade 3 or higher TLS
- neurologic events considered related to AMG 420 by the investigator and meeting one or more of the following criteria:
  - grade 3 neurologic event leading to treatment interruption and has not resolved to  $\leq$  grade 1 within 14 days despite infusion interruption
  - grade 3 neurologic event that recurs after dose reduction
  - grade 4 neurologic event
- DLT or other unmanageable toxicity unless a subject has a clear clinical benefit from treatment, the toxicity has resolved to  $\leq$  grade 1 or baseline and after consultation with the sponsor
- in case of re-appearance of the same grade 4 adverse event
- treatment interruption of more than 2 weeks or several interruptions exceeding a total of 14 days of treatment per cycle due to serious adverse events/adverse events
- possible DILI requiring permanent withholding as per [Section 7.4.3](#)
- non-manageable GvHD
- subjects who require more than 1 dose reduction
- disease progression as defined by revised IMWG response criteria

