#### **7.4.3 Hepatotoxicity Stopping and Rechallenge Rules**

Refer to [Section 12.7](#) for details regarding DILI injury guidelines, as specified in the Guidance for Industry Drug-Induced Liver Injury: Premarketing Clinical Evaluation, July 2009.

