### Criteria for Withholding and/or Permanent Discontinuation of Amgen Investigational Product and Other Protocol-required Therapies Due to Potential Hepatotoxicity

The following stopping and/or withholding rules apply to subjects for whom another cause of their changes in liver biomarkers (TBL, INR and transaminases) has not been identified.

Important alternative causes for elevated AST/ALT and/or TBL values include, but are not limited to:

- Hepatobiliary tract disease
- Viral hepatitis (eg, hepatitis A/B/C/D/E, Epstein-Barr Virus, cytomegalovirus, herpes simplex virus, varicella, toxoplasmosis, and parvovirus)
- Right sided heart failure, hypotension or any cause of hypoxia to the liver causing ischemia
- Exposure to hepatotoxic agents/drugs or hepatotoxins, including herbal and dietary supplements, plants and mushrooms
- Heritable disorders causing impaired glucuronidation (eg, Gilbert's syndrome, Crigler-Najjar syndrome) and drugs that inhibit bilirubin glucuronidation (eg, indinavir, atazanavir)
- Alpha-one antitrypsin deficiency
- Alcoholic hepatitis
- Autoimmune hepatitis
- Wilson's disease and hemochromatosis
- Nonalcoholic fatty liver disease including steatohepatitis
- Non-hepatic causes (eg, rhabdomyolysis, hemolysis)

If investigational product(s) is/are withheld, the subject is to be followed for possible drug-induced liver injury (DILI) according to recommendations in the last section of this appendix.

Rechallenge may be considered if an alternative cause for impaired liver tests (ALT, AST, ALP) and/or elevated TBL, is discovered and the laboratory abnormalities resolve to normal or baseline (see next section in this appendix).

**Table 12-2. Conditions for Withholding and/or Permanent Discontinuation of Amgen Investigational Product and Other Protocol-required Therapies Due to Potential Hepatotoxicity**

Analyte	Temporary Withholding	Permanent Discontinuation
TBL	> 3x ULN at any time	> 2x ULN
		OR
INR	--	> 1.5x (for subjects not on anticoagulation therapy)
	OR	AND
AST/ALT	> 8x ULN at any time > 5x ULN but < 8x ULN for ≥ 2 weeks > 5x ULN but < 8x ULN and unable to adhere to enhanced monitoring schedule > 3x ULN with clinical signs or symptoms that are consistent with hepatitis (such as right upper quadrant pain/tenderness, fever, nausea, vomiting, and jaundice)	In the presence of no important alternative causes for elevated AST/ALT and/or TBL values > 3x ULN (when baseline was < ULN)
	OR	
ALP	> 8x ULN at any time	--

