ALP = alkaline phosphatase; ALT = alanine aminotransferase; AST = aspartate aminotransferase; INR = international normalized ratio; TBL = total bilirubin; ULN = upper limit of normal

**Criteria for Rechallenge of Amgen Investigational Product and Other Protocol-required Therapies After Potential Hepatotoxicity**

The decision to rechallenge the subject is to be discussed and agreed upon unanimously by the subject, investigator, and Amgen.

If signs or symptoms recur with rechallenge, then Amgen investigational product is to be permanently discontinued. Subjects who clearly meet the criteria for permanent discontinuation (as described in [Table 12-2](#)) are never to be rechallenged.

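### After cycle 1, Table 12-2 sets no mandatory liver hold or stop for a combined AST/ALT and bilirubin or INR rise when that transaminase was already at or above ULN at baseline

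*Protocol*

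**What the plan says.** - **Entry.** Protocol 6.1, criterion 108, sets the limit for "aspartate aminotransferase (AST) and alanine aminotransferase (ALT") at below 3x ULN, so a baseline from 1x to just under 3x ULN is eligible.
- **Permanent stop.** Protocol 12.7, Table 12-2, requires it for TBL > 2x ULN or INR > 1.5x (not on anticoagulation) together with AST/ALT "> 3x ULN (when baseline was < ULN"), where no important alternative cause exists. There is no line for a higher baseline.
- **Temporary hold.** The same table requires one for TBL > 3x ULN, AST/ALT > 8x, AST/ALT between 5x and 8x that lasts 2 weeks or cannot be monitored closely, AST/ALT > 3x with signs or symptoms of hepatitis, or ALP > 8x. The INR cell in this column is a dash.
- **Cycle 1.** In 7.4.1, "Any subject meeting the criteria for Hy's Law case" counts as a DLT, with no baseline condition. The DLT period "will be the 4 weeks on AMG 420 treatment within the first treatment cycle". SAP section 5 likewise requires a DLT to start within 28 days of first dose.
- **Cross-references.** The permanent-discontinuation list in 7.4.2.1.3 includes "possible DILI requiring permanent withholding as per" Section 7.4.3. Section 7.4.3 has no thresholds and sends the reader to 12.7 "for details regarding DILI injury guidelines".
- **Rechallenge.** "Subjects who clearly meet the criteria for permanent discontinuation" in Table 12-2 may never be rechallenged. After a hold, 12.7 allows rechallenge to be considered if another cause is found and the values return to normal or baseline.
- **Observation.** AST or ALT > 3x ULN, or a doubling of a raised baseline, requires close observation. Retesting is every 24 hours while TBL is > 2x ULN or INR > 1.5.

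**The concern.** Two subjects with the same laboratory values in cycle 2 or later are handled in opposite ways, depending only on whether the transaminase was just below or just above ULN before treatment. One must stop for good and may not be rechallenged. For the other, the table requires neither a hold nor a stop, and the continuous infusion may go on under observation unless the investigator acts. The subjects without a rule are those who entered with abnormal liver tests. The protocol treats the same pattern as dose-limiting in cycle 1 whatever the baseline, so the difference in later cycles is hard to explain as intended.

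Liver changes are foreseeable with this drug. The protocol lists transaminitis and hyperbilirubinemia among CRS signs (3.3.3 and 7.4.2.1.2.5) and elevated liver enzymes among reactions to blinatumomab (3.2.2.4).

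**Working it through.** The plan states no figure on this point, so the check applies its rules to laboratory values. All values are multiples of ULN, except INR. Every profile has no hepatitis signs or symptoms, ALP not above 8, no anticoagulation and no alternative cause.

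**Rules as written**

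- Stop (Table 12-2) = (TBL > 2 or INR > 1.5) and AST/ALT > 3 and baseline < 1.
- Hold (Table 12-2) = TBL > 3; or AST/ALT > 8; or AST/ALT 5 to 8 for at least 2 weeks or without enhanced monitoring; or AST/ALT > 3 with hepatitis signs or symptoms; or ALP > 8.
- Hy's Law DLT (7.4.1) = inside the 4-week window, AST or ALT ≥ 3 and (TBL > 2 or INR > 1.5), without cholestasis.
- Close observation (12.7) = AST or ALT > 3, among other triggers.

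**One case.** AST 4, TBL 2.5, cycle 2.

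- Baseline 0.9: 2.5 > 2, 4 > 3 and 0.9 < 1, so permanent stop.
- Baseline 1.1: 1.1 is not < 1, so no stop. TBL 2.5 is not > 3 and AST 4 is not > 5, so no hold. Close observation applies because 4 > 3.

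**Grid.** AST/ALT of 3.1, 4 and 5 were each combined with six bilirubin and INR settings: TBL 2.1, 2.5 or 3.0 with INR 1.0; INR 1.6 or 3.0 with TBL 1.0; and TBL 2.5 with INR 1.8. That is 3 × 6 = 18 profiles.

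| Baseline | Inside DLT window | After DLT window |
|---|---|---|
| 0.8 | 18 of 18 permanent stop | 18 of 18 permanent stop |
| 1.0, 1.5, 2.0, 2.9 (each) | 18 of 18 Hy's Law DLT | 0 of 18 hold or stop; 18 of 18 close observation |

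**Edges of the gap**

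- AST/ALT 7 for less than 2 weeks under monitoring, TBL 2.5, baseline 1.5: still no hold or stop, so the gap extends into the 5x to 8x range.
- AST/ALT 4, TBL 2.5, baseline 1.5, with hepatitis symptoms or with ALP 9: temporary hold. Those subjects are outside the gap.

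**With the proposed line** (hold if AST or ALT > 3 and above baseline, with TBL > 2 or INR > 1.5): every profile has AST/ALT of at least 3.1, which exceeds both 3 and the highest baseline tested (2.9). Every profile also has TBL > 2 or INR > 1.5. The result is 18 of 18 holds at each raised baseline.

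**The case against.** **The DLT boundary is not perfectly clean.** Table 7-2 refers to DLT criteria without a cycle limit. Protocol 10.4.2.3.1 and SAP 9.6.2 plan a sensitivity analysis of DLTs outside the window. The item in 7.4.2.1.3 on a DLT or other unmanageable toxicity carries no time limit. A sponsor could argue that a later Hy's Law case falls under that item. These looser uses do not override the explicit window in 7.4.1 and the SAP, and that item also allows continuation for clear clinical benefit once the toxicity has resolved and the sponsor has been consulted.

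**The subjects are not unprotected.** A reader might infer that raised-baseline subjects have no liver safeguard at all. The documents do not support that. Close observation and daily retesting are mandatory, symptomatic cases must be held, grade 4 events require interruption, CRS rules may apply, and the investigator may stop treatment on medical judgement. What is missing is a mandatory liver-specific hold or stop.

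**AST and ALT may differ.** If AST was 1.1x ULN at baseline but ALT was normal, a rise of ALT above 3x ULN arguably still meets the permanent rule. This stands, and it limits the gap to the transaminase that was itself raised.

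**The check shows coverage only.** The raised-baseline profiles were chosen inside the gap, so zero after the window follows by construction. A reader might also infer a risk from the first-in-human study: protocol 3.2.2.4 lists no hepatic DLT or drug-related hepatic serious event among 35 subjects, and the exact two-sided 95% upper limit is 1 − 0.025^(1/35) = 10.0%. That limit describes a different event in a different group and is not a rate for this gap.

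**Little future exposure.** The Amendment 5 rationale records termination of the program and no further drug supply. That lowers the yield of a change. The same amendment still revised cycle-delay and COVID dosing rules, so continued dosing was foreseen.

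**Conclusion.** The gap is real. It covers a subject whose rising transaminase was at or above ULN at baseline, after the cycle 1 DLT window, without hepatitis signs or symptoms or an alternative cause, and with ALP not above 8x ULN. The values concerned are AST or ALT > 3x to 5x ULN, or 5x to 8x for less than 2 weeks under monitoring, with TBL > 2x to 3x ULN or INR > 1.5.

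The documents do not give the number of such subjects. With about 20 enrolled it is probably small, and no event rate can be derived. The point deserves correction because following the table as written gives the weaker response to subjects with abnormal liver tests at entry, and tests already collected would close the gap.

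The conclusion rests on reading the Table 12-2 cell literally; it reads as complete and is not marked as redacted. The external guidance that 12.7 cites was not available. CTCAE cut-offs are not printed in the documents, so the profiles were not graded against Table 7-2.

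**What to change.** 1. **Add a line to Table 12-2 for baseline ≥ ULN, applied to AST and ALT separately.** AST or ALT > 3x ULN and above its own baseline, with TBL > 2x ULN or INR > 1.5x (not on anticoagulation) and no alternative cause, requires an immediate temporary hold.
2. **State the restart rule in the same line.** Restart only if values return to baseline within the existing 14-day limit and the subject, investigator and sponsor agree; otherwise discontinue permanently. This is needed because 12.7 ties rechallenge to finding another cause, which these subjects lack, and 7.4.2.1.3 ends treatment after a "treatment interruption of more than 2 weeks or several interruptions exceeding a total of 14 days of treatment per cycle" for adverse events.
3. **Clarify the DILI reporting paragraph in 12.7.** It refers back to the criteria above without saying whether the baseline limit carries over. State that the 24-hour report applies whatever the baseline.

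Simply deleting the baseline qualifier would be too blunt: a change from 2.9x to 3.1x ULN (3.1/2.9 = 1.07-fold) with qualifying bilirubin would then force a permanent stop.

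An immediate permanent stop at 2x baseline or more is an option for the sponsor to decide, because 12.7 uses that multiple only to trigger observation. The threshold would be max(3, 2 × baseline): 3x ULN for baselines 1.1x and 1.5x, 4x for 2.0x, 5x for 2.5x and 5.8x for 2.9x. Crossing those five baselines with AST 3.1x, 4.0x and 4.9x at TBL 2.5x ULN gives 15 cases: 8 permanent stops (3 + 3 + 2 + 0 + 0) and 7 holds (0 + 0 + 1 + 3 + 3).

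**Cost.** No new tests are needed, but it takes a protocol amendment, with ethics approval where necessary, across about 15 sites. The clinical downside is an occasional hold in a raised-baseline subject, and some of those holds will become permanent stops.

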**Drug-induced Liver Injury Reporting and Additional Assessments**  
Reporting

To facilitate appropriate monitoring for signals of DILI, cases of concurrent AST or ALT and TBL and/or INR elevation, according to the criteria specified in the above, require the following:

- The event is to be reported to Amgen as a serious adverse event within 24 hours of discovery or notification of the event (ie, before additional etiologic investigations have been concluded)
- The appropriate Case Report Form (CRF) (eg, Event CRF) that captures information necessary to facilitate the evaluation of treatment-emergent liver abnormalities is to be completed and sent to Amgen

Other events of hepatotoxicity and potential DILI are to be reported as serious adverse events if they meet the criteria for a serious adverse event defined in [Section 12.4](#).

#### Additional Clinical Assessments and Observation

All subjects in whom investigational product(s) or protocol-required therapies is/are withheld (either permanently or conditionally) due to potential DILI as specified in [Table 12-2](#) or who experience AST or ALT elevations > 3 x upper limit of normal (ULN) or 2-fold increases above baseline values for subjects with elevated values before drug are to undergo a period of “close observation” until abnormalities return to normal or to the subject’s baseline levels.

#### Assessments that are to be performed during this period include:

- Repeat AST, ALT, ALP, bilirubin (BIL) (total and direct), and INR within 24 hours
- In cases of TBL > 2x ULN or INR > 1.5, retesting of liver tests, BIL (total and direct), and INR is to be performed every 24 hours until laboratory abnormalities improve

Testing frequency of the above laboratory tests may decrease if the abnormalities stabilize or the investigational product(s) or protocol-required therapies has/have been discontinued AND the subject is asymptomatic.

Initiate investigation of alternative causes for elevated AST or ALT and/or elevated TBL.

The following are to be considered depending on the clinical situation:

- Complete blood count with differential to assess for eosinophilia
- Serum total immunoglobulin (Ig)G, anti-nuclear antibody anti-smooth muscle antibody, and liver kidney microsomal antibody-1 to assess for autoimmune hepatitis
- Serum acetaminophen (paracetamol) levels

- A more detailed history of:
  - Prior and/or concurrent diseases or illness
  - Exposure to environmental and/or industrial chemical agents
  - Symptoms (if applicable) including right upper quadrant pain, hypersensitivity-type reactions, fatigue, nausea, vomiting and fever
  - Prior and/or concurrent use of alcohol, recreational drugs and special diets
  - Concomitant use of medications (including non-prescription medicines and herbal and dietary supplements), plants, and mushrooms
- Viral serologies
- Creatine phosphokinase, haptoglobin, lactate dehydrogenase and peripheral blood smear
- Appropriate liver imaging if clinically indicated
- Appropriate blood sampling for pharmacokinetic analysis if this has not already been collected
- Hepatology consult (liver biopsy may be considered in consultation with a hepatologist)

Follow the subject and the laboratory tests (ALT, AST, TBL, INR) until all laboratory abnormalities return to baseline or normal or considered stable by the investigator. The “close observation period” is to continue for a minimum of 4 weeks after discontinuation of all investigational product(s) and protocol-required therapies.

The potential DILI event and additional information such as medical history, concomitant medications and laboratory results must be captured in the corresponding CRFs.

